8.1 Analysis Populations

Intent-to-treat (ITT): all subjects who were randomized

Per protocol (PP): all subjects who completed Stage 1, underwent assessment of anxiety symptoms, and did not experience a major protocol deviation

Crossover: all subjects who completed Stage 2 in addition to completing Stage 1

Safety: all subjects who receive any study treatment

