A = At the beginning of the session; B = Approximately every sixty minutes; C = As needed; D = Approximately six hours post drug; E = Day 2 and Day 7 phone calls only; F = Reactions collected for seven days post experimental session; G = Independent Rater administered; H = May be recorded to video; I = Stage 2 subjects only; J = Only MDMA subjects will terminate.

Table 3. Time & Events Stage 2

Study Phase	Experimental Session	Integrative Sessions			Experimental Session	Integrative Sessions		
	V15	V16	V17	V18	V19	V20	V21	V22
Visit #	V15	V16	V17	V18	V19	V20	V21	V22
Visit Timing		1 day later	2 Wks later	2 Wks later	Appr. 1 Month after V15	1 day later	2 Wks later	2 Wks later
LSAS		✓ ^G	✓ ^G	✓ ^G		✓ ^G	✓ ^G	✓ ^G
C-SSRS	✓ ^{A, C, D}	✓ ^E	✓	✓	✓ ^{A, C, D}	✓ ^E	✓	✓
Feedback Questionnaire, Qualitative Interview								✓
Collect Concomitant Medication	✓	✓	✓	✓	✓	✓	✓	✓
End Medication Taper (if applicable)	✓ ^I							
Collect Serology Samples (OT, AVP, CORT)	✓			✓	✓			✓
Record to Video	✓	✓	✓	✓	✓	✓	✓	✓
General Wellbeing	✓	✓	✓	✓	✓	✓	✓	✓
Drug Screen	✓				✓			
Pregnancy Screen (if applicable)	✓				✓			
BDI-II, STAI		✓	✓	✓		✓	✓	✓
PSS		✓				✓		✓
IRI, RSES		✓				✓		✓
TASIT	✓				✓			✓
ERQ, TAS-20								✓
Administer Drug + Therapy	✓				✓			
Monitoring of BP, Pulse, and Temperature, SUD	✓ ^{A, B, C}				✓ ^{A, B, C}			
Integrative Therapy Session		✓	✓	✓		✓	✓	✓
Start 7 Days Integrative Phone Contact		✓				✓		
Spont. Reported Reactions & All Adverse Events	✓	✓ ^F	✓		✓	✓ ^F	✓	
Symptoms at Baseline	✓	✓	✓	✓	✓	✓	✓	✓
Adverse Events Requiring Doctor's Visit	✓	✓	✓	✓	✓	✓	✓	✓
Adverse Events Causing Withdrawal	✓	✓	✓	✓	✓	✓	✓	✓
SAEs	✓	✓	✓	✓	✓	✓	✓	✓
Termination								✓
Approximate Hours for Study Visit	8.0	1.9	1.7	2.1	8.0	1.9	1.7	2.7

A = At the beginning of the session; B = Approximately every sixty minutes; C = As needed; D = Approximately six hours post MDMA; E = Day 2 and Day 7 phone calls only; F = Reactions collected for seven days post experimental session; G = Independent Rater administered; H = May be recorded to video; I = At least 5 half-lives and 1 week before the experimental session.

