2.0 Introduction

This document presents a Statistical Analysis Plan (SAP) for MAPS study protocol MAA-1, a Phase 2 pilot clinical trial designed to evaluate the safety, feasibility, and efficacy of MDMA-assisted psychotherapy in treating social anxiety in adults on the autism spectrum.

The Multidisciplinary Association for Psychedelic Studies (MAPS) is a non-profit research and educational organization working to obtain approval for the prescription use of 3,4-methylenedioxymethamphetamine (MDMA)-assisted psychotherapy in adults on the autism spectrum with social anxiety. This is an initial pilot study to assess the efficacy of MDMA for this indication, following promising results from MAPS-sponsored studies of MDMA-assisted psychotherapy for posttraumatic stress disorder (PTSD).

The Phase 2 pilot study will examine the safety, feasibility, and efficacy of MDMA-assisted psychotherapy for social anxiety in 12 MDMA-naïve adults on the autism spectrum. This study is designed as a dose escalation study to assist with the exploration of safety and finding the most effective dose in this population. Subjects assigned to the MDMA group will receive two of three different doses, either 75 mg, 100 mg, or 125 mg MDMA. Overall, eight subjects (66.7%) will be randomized to the MDMA group and four subjects (33.3%) will be randomized to the placebo group. Subjects who received the placebo during Stage 1 will have the opportunity to cross over and take part in a second study segment, referred to as Stage 2, with two open-label experimental sessions, after completing the six-month follow-up visit at the end of Stage 1.

This study is designed to obtain safety data, and secondarily estimates of effect size for efficacy. The data will be used to determine study design and dosing for future studies for this indication. MAA-1 is also intended to contribute to the development of a manualized psychotherapeutic approach to this potential treatment. This study is exploratory. As a result, the sponsor will perform tests on all statistical comparisons without correcting for multiple comparisons.

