3.2 Secondary Objectives

The following objectives will compare MDMA and placebo groups in the blinded Stage 1:

- To assess effects on levels of oxytocin (OT), arginine vasopressin (AVP), and cortisol (CORT) in peripheral blood at baseline, once during each experimental session between hours 2 – 3, one month after the second experimental session, and at 6-month follow-up.
- To assess effects on social perception using The Awareness of Social Inference Test (TASIT) at baseline, once during each experimental session between hours 2-3, one month after the second experimental session, and at 6-month follow-up.

- To assess effects on emotion labeling using the Toronto Alexithymia Scale-20 (TAS-20) at baseline, one month after each experimental session, and 6-month follow-up.
- To assess effects on emotion regulation using the Emotion Regulation Questionnaire (ERQ) at baseline, one month after each experimental session, and 6-month follow-up.
- To assess effects on depression symptoms as measured by the Beck Depression Inventory-II (BDI-II) at baseline, one day, two weeks, one month after each experimental session, monthly by mail during the 5 months leading up to the 6-month follow-up assessment.
- To assess effects on perceptions of stress as measured by the Perceived Stress Scale (PSS) at baseline, within 24 hours after each experimental session, one month after each experimental session and monthly by mail leading up to the 6-month follow-up assessment.
- To assess effects on four aspects of empathy, as measured by the Interpersonal Reactivity Index (IRI) at baseline, within 24 hours after each experimental session, one month after each experimental session, and at the 6-month follow-up assessment.
- To assess effects on self-esteem as measured by the Rosenberg Self-Esteem Scale (RSES) at baseline, within 24 hours after each experimental session, one month after each experimental session, and at the 6-month follow-up assessment.
- To assess effects on state and trait anxiety as measured by the State-Trait Anxiety Index (STAI Form Y) at baseline, one day, two weeks, and one month after each experimental session, and monthly by mail leading up to the 6-month followup assessment.

The following objectives will compare effects in specified subjects:

- To determine if subjects who receive placebo in Stage 1 show a reduction in LSAS scores after two open-label sessions in the Stage 2 crossover

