8.10.2.1 Secondary Efficacy Analyses at Secondary Endpoints

Crossover Subject Analyses

LSAS data from subjects assigned to the placebo group, i.e. ‘crossover population,’ will be analyzed by t-tests on difference scores from Stage 1 endpoint (Visit 13) to Stage 2 endpoint (Visit 22) only if there is sufficient data to examine.

6-month Follow-up Analyses

To determine durability of effects, LSAS data will be analyzed by t-tests on difference scores from Stage 1 endpoint (Visit 13) to 6-month follow-up. Additionally, the following measures’ scores will be analyzed in this same fashion: PSS, BDI-II, IRI, RSES, STAI, TASIT, TAS-20, ERQ, QoL-Q

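### The SAP defines the Crossover population in two ways, and the completer-only version can bias the Stage 2 LSAS result if anyone stops open-label treatment

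*SAP*

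**What the plan says.** SAP 8.1 lists four populations. ITT depends on randomization and Safety on receiving treatment. The one for Stage 2 depends on finishing: "Crossover: all subjects who completed Stage 2 in addition to completing Stage 1". What counts as completing Stage 2 is not defined.

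SAP 8.10.2.1 uses the same label differently. It takes "LSAS data from subjects assigned to the placebo group, i.e". the crossover population, with no completion condition, and tests the LSAS change from Visit 13 to Visit 22, "only if there is sufficient data to examine". No threshold for sufficiency is given.

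The objective served is in SAP 3.2: whether placebo subjects "show a reduction in LSAS scores after two open-label sessions in the Stage 2 crossover".

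SAP 8.2 assigns early-termination data to a scheduled visit, but only for ITT and Safety variables.

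The protocol is wider. Section 12.0 compares Stage 1 with Stage 2 in extension subjects and does not restrict this to completers. Section 5.4 promises an intent-to-treat analysis of whatever data exist for subjects who leave after the first experimental session, but gives no rule specific to Stage 2. Protocol Table 3 has the Independent Rater score LSAS at V16, V17 and V18 after the first open-label session and at V20, V21 and V22 after the second.

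**The concern.** Under 8.1, membership is settled by something that happens after open-label treatment begins. A subject who has the first Stage 2 session and goes no further may have up to three rated LSAS scores, yet falls outside the set. Stage 1 also has a completer-type population (PP), but ITT stands beside it. Stage 2 has no second efficacy set.

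The loss could also be hard to see. SAP 8.0 sends data that the plan does not analyse to listings only. The disposition tabulation in SAP 8.7 names Safety, ITT and PP, but neither Crossover nor the number who started Stage 2.

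At stake is a named secondary objective, answered by a before-and-after change in very few people with no concurrent control. In that setting, one person's inclusion can move the mean materially.

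**Working it through.** **Does another rule bring the stopper back?**

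- SAP 8.10.2.1, read literally, would include the stopper. It contradicts 8.1, and it would also take in placebo subjects who decline Stage 2, which Protocol 5.2.8 makes voluntary.
- Even on that reading, the outcome is a Visit 13 to Visit 22 difference. A stopper without a Visit 22 score has no value to contribute.
- SAP 8.2 would supply a value for ITT or Safety variables, but does not name Crossover.

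So under 8.1 the stopper is out. Under 8.10.2.1 the stopper is nominally in, but is lost unless Visit 22 was collected.

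**Number at risk.** The plan states no effect size, power or dropout figure for Stage 2, so only the count can be reproduced. The dose regimen table gives 2 + 2 = 4 placebo subjects, and 4/12 = 33.3%, which agrees with SAP 2.0: "four subjects (33.3%) will be randomized to the placebo group". If all four enter, each stopper is 1/4 = 25% of the set.

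**Effect on the mean.** Let four subjects enter and *k* stop. Let *m* be the completers' mean LSAS improvement and *r* × *m* the stoppers' improvement. Both *k* and *r* are assumptions.

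All-treated mean = [(4 − *k*)*m* + *k r m*]/4, so completer mean ÷ all-treated mean = 4/(4 − *k* + *k r*).

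| *r* | one stopper | two stoppers |
|---|---|---|
| −0.5 | 4/2.5 = 1.60 | 4/1 = 4.00 |
| 0 | 4/3 = 1.33 | 4/2 = 2.00 |
| 0.5 | 4/3.5 = 1.14 | 4/3 = 1.33 |
| 1 | 4/4 = 1.00 | 4/4 = 1.00 |
| 1.5 | 4/4.5 = 0.89 | 4/5 = 0.80 |

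In points, if three completers improve by 20 and the stopper by 0 (assumed), the completer mean is 20 and the all-treated mean is (3 × 20 + 0)/4 = 15. With *k* = 0 the two means are the same.

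**Effect on precision.** SAP 8.0 makes tests two-sided. The 0.05 level is stated for the primary analysis and borrowed here. For a one-sample t interval on difference scores, the 95% half-width is t/√n in units of the SD of the change:

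- n = 4: 3.182/√4 = 1.59 SD
- n = 3: 4.303/√3 = 2.48 SD

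**The case against.** **Bias is not established.** It needs someone to stop, no usable Visit 22 score, and a stopper who fared differently from the completers. The documents give no Stage 2 dropout rate. This stands. With one stopper, the range shown above runs from 60% too high, through no difference, to 11% too low.

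**Stoppers need not be poor responders.** A reader might infer that the completer rule strips out exactly those who did worst and so overstates the effect. The documents do not support that. The reasons they give for ending treatment include pregnancy, a psychiatric diagnosis or a need for excluded medication (Protocol 5.4), a drug-related SAE (2.4), medical complications (7.2.1), and toxicity or hyponatremia (7.2.6). None is defined by LSAS response.

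**Stopping drug is not the same as leaving the study.** Protocol 2.4, 5.4 and 7.2.1 keep such subjects under assessment where possible, so a subject who misses the second dose may still have Visit 22 and might be read as having completed. This also stands, and it is a reason to define completion and to use Visit 22 wherever it exists.

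**A last-score mean has its own flaw.** It would mix a next-day score after one session with one-month scores after two, whereas the objective concerns two sessions. This is enough to keep it out of the main estimate.

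**The reach is small, and little is hidden.** The analysis is uncontrolled and conditional, in a trial declared exploratory. Individual scores go into listings, SAP 8.7 reports study discontinuations with reasons, and anyone treated stays in the Safety population. That limits the consequence, but it does not reconcile two definitions of one population.

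**Conclusion.** The point holds as a definitional conflict with a possible bias. SAP 8.1 and 8.10.2.1 disagree on who is in the Crossover population, completion is undefined, and no early-termination rule reaches Stage 2. Read as written, 8.1 is narrower than the comparison the protocol describes.

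The size depends on assumptions that the documents cannot settle: that four enter, how many stop, and how they fared. With one stopper, the completer mean is between 1.60 and 0.89 times the all-treated mean for *r* from −0.5 to 1.5, and is too high only if *r* is below 1. If the stopper had improved as much as the completers, the mean would not move, but the interval would still widen.

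This should be corrected before analysis, but it does not threaten the trial's main result. The primary comparison is the randomized Stage 1 change at Visit 13 (SAP 8.10.1), which does not use this population.

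**What to change.** - In both SAP 8.1 and 8.10.2.1, define Crossover as all placebo-arm subjects who receive at least one Stage 2 dose.
- Use the Visit 22 LSAS whenever it was collected, including from subjects who stopped dosing but stayed for assessment.
- For subjects without Visit 22, show each available Stage 2 LSAS with its visit. Give an all-treated estimate using the last post-dose score as a sensitivity analysis, not as the main result.
- Keep the completer-only result as supporting, and state what completion of Stage 2 means.
- Report the numbers entering, stopping and completing Stage 2.

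The cost is SAP wording. The scores are already scheduled, so no extra visit or assessment is needed. The downside is that a stopper's last score may come before Visit 22 and after one session only, which is why it is labelled by visit and kept to the sensitivity analysis. If every subject who starts Stage 2 completes it, the result is the same under either definition.

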8.2 Handling of Dropouts, Missing Data

Early termination visit data for ITT and Safety variables will be analyzed at the closest scheduled visit. If the closest visit has valid data, the early termination data will be assigned to the next available visit.

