4.1 Planned Duration of Study

- Subjects in Stage 1 and follow-up: 8 months
- Subjects in Stage 1, follow-up, and Stage 2: 10 months

These lengths of time do not include screening, which may take up to two months. The total duration of the study will depend on enrollment rates, but is expected to last at least 22 months. Any delay between visits would result in a corresponding extension of study duration.

Table 2. Time & Events Stage 1

Study Phase	Baseline		Preparatory Sessions			Experimental Session	Integrative Sessions			Experimental Session	Integrative Sessions			Follow-up	6-Month Follow-up
	V1	V2	V3	V4	V5	V6	V7	V8	V9	V10	V11	V12	V13	(remote)	V14
Visit Timing			Week 1	Week 2	Week 3		1 day later	2 Wks later	2 Wks later	Apr. 1 Month after V6	1 day later	2 Wks later	2 Wks later	Monthly By Mail	6 Months after V10
Informed Consent	✓														
Medical/Psychiatric History & Evaluation	✓														
SCID	✓														
General Physical Exam (includes neurological)		✓													
Screening Clinical Lab Tests, EKG		✓													
ADOS-2		✓ ^H													
LSAS		✓ ^{G,H}					✓ ^G	✓ ^G	✓ ^G		✓ ^G	✓ ^G	✓ ^G		✓ ^G
C-SSRS		✓			✓	✓ ^{A,C,D}	✓ ^E	✓	✓	✓ ^{A,C,D}	✓ ^E	✓	✓		✓
Feedback Questionnaire, Qualitative Interview		✓													✓
Study Enrollment if Eligible			✓												
Collect Concomitant Medication	✓		✓	✓	✓	✓	✓	✓	✓	✓	✓	✓	✓		✓
Start Medication Taper (if applicable)			✓												✓ ^I
Collect Serology Samples (OT, AVP, CORT)		✓								✓			✓		✓
Record to Video			✓	✓	✓	✓	✓	✓	✓	✓	✓	✓	✓		✓
General Wellbeing			✓	✓	✓	✓	✓	✓	✓	✓	✓	✓	✓		✓
Pregnancy Screen (if applicable), Drug Screen		✓				✓				✓					
BDI-II, STAI			✓				✓	✓	✓		✓	✓	✓	✓	✓
PSS			✓				✓				✓		✓	✓	✓
IRI, RSES			✓				✓				✓		✓		✓
TASIT				✓		✓				✓			✓		✓
ERQ, TAS-20					✓								✓		✓
QoL-Q					✓										✓
Administer Drug + Therapy						✓				✓					
Monitoring of BP, Pulse, and Temperature, SUD						✓ ^{A,B,C}				✓ ^{A,B,C}					
Belief of Condition Assignment							✓				✓				
Integrative Therapy Session							✓	✓	✓		✓	✓	✓		
Start 7 Days Phone Contact							✓				✓				
Spont. Reported Reactions & All Adverse Events						✓	✓ ^F	✓		✓	✓ ^F	✓			
Symptoms at Baseline	✓		✓	✓	✓	✓	✓	✓	✓	✓	✓	✓	✓		✓
Adverse Events Requiring Doctor's Visit			✓	✓	✓	✓	✓	✓	✓	✓	✓	✓	✓		✓
Adverse Events Causing Withdrawal, SAEs			✓	✓	✓	✓	✓	✓	✓	✓	✓	✓	✓	✓	✓
Unblinding & Termination															✓ ^J
Approximate Hours for Study Visit	3	1.8	1.5	1.5	1.8	8.0	1.9	1.7	2.1	8.0	1.9	1.7	2.6	0	2.2

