5.4 Removal of Subjects from the Study

Subjects can withdraw consent at any time without prejudice. The therapists can withdraw a subject if, in their clinical judgment, it is in the best interest of the subject or if the subject cannot comply with elements of the protocol that are critical for safety or for the scientific integrity of the study. If the therapists withdraw a subject from the study, the therapists will explain the reason for withdrawing the subject. The reason for early termination will be recorded in the subject's Source Records and CRF.

If a subject develops any exclusion criteria that in the opinion of the Medical Monitor, affects the safety of the subject, including psychiatric diagnosis, pregnancy, or requiring use of excluded medications, the subject will discontinue treatment but remain in the study for follow-up purposes. Whenever possible, the tests and evaluations listed for the follow-up will be carried out. Efforts will be made to obtain information about AE outcomes, if deemed necessary by the PI, Data Safety Monitor, Medical Monitor, and/or sponsor.

Subjects discontinuing treatment before the first experimental session will be replaced until blinded data has been collected from 12 subjects. Subjects who discontinue participation after the first experimental session will not be replaced, and an intent-to-treat analysis will be conducted with all available data. Subjects discontinuing treatment prior to the second experimental session will be asked to complete integrative therapy sessions, outcome assessments prior to discontinuation and complete the six-month follow-up assessment if possible. The blind will not be broken for these subjects until after the six-month follow-up assessments have been completed.

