Biomarkers will be evaluated for predictive and prognostic power. Separate estimates of effect size will be performed for OT, AVP and CORT. Changes in biomarker concentrations from pre-treatment levels will be used to analyze effects of acute dosing and to determine the time-course of elevated OT and AVP levels post-drug. Pre-treatment biomarker concentrations will be evaluated for predictive power using an exploratory hierarchical regression analysis with condition assignment in Stage 1 and biomarker concentrations at baseline as predictors and treatment outcomes as dependent variables. One regression will be performed with biomarker values taken at the second experimental session. A second regression will be performed on biomarker values taken two weeks after the second experimental session.

TAS-20 scores will be evaluated for predictive power using an exploratory hierarchical regression analysis with condition assignment in Stage 1 and TAS-20 scores at baseline as predictors and with LSAS scores as dependent measures. One regression will examine the predictive power of condition and baseline TAS-20 scores upon LSAS scores one month after the first experimental session and the other will investigate whether condition and baseline TAS-20 and will predict LSAS score at one month after the second experimental session.

Subjects who discontinue treatment prior to the second experimental session will be asked to complete the final outcome assessment prior to continuing to the 6-month follow-up whenever possible. The data from these subjects will be tested for equivalence to data from subjects completing the study per protocol. If found to be equivalent, data from these subjects will be combined for an exploratory intent-to-treat effect size estimate to examine results without bias towards subjects more likely to complete the study per protocol.

Stage 1 and Stage 2 outcomes in extension subjects will be compared after the outcome measure assessments are complete for all extension subjects.

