8.0 Analyses

In general, nominal variables will be described in terms of frequencies and percentages and analyzed using chi square analysis. Ordinal and non-normal continuous variables will be described using sample median and range, and analyzed by non-parametric statistical tests, and approximately normal variables will be described using sample mean and standard deviations and analyzed by parametric statistical tests. All statistical tests will be two-sided. All p-values will be rounded to and displayed in four decimals. If a p-value less than 0.0001 occurs it will be shown in tables as <0.0001. For any analysis that is called out as parametric, e.g. t-test, the parametric assumptions will be examined. If necessary, nonparametric analyses will be utilized, e.g. Wilcoxon rank-sum test.

Clinical data will be presented in tabular format. Data not subject to analysis according to this plan will not appear in any tables or graphs, but will be included in the data listings. Analyses will be carried out with SAS Version 9.3 or higher. Selected results may be presented graphically using standard graphical software.

Post-hoc exploratory analyses not identified in this SAP may be performed to further examine the study data. These analyses will be clearly identified as such in the final clinical study report.

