8.10.1 Primary Efficacy Analyses

Liebowitz Social Anxiety Scale (LSAS)

The primary efficacy evaluation is the change from baseline to the primary outcome timepoint (visit 13, one month post experimental session 2) in the LSAS score of Social Anxiety (difference score). The primary efficacy comparison on difference scores will be made with independent sample t-tests at an alpha level of 0.05. If the primary hypothesis rejects, pairwise comparisons among the treatment groups will be made with t-tests. If the parametric assumptions for the t-test analyses are not met, the analogous nonparametric methods will be used (Wilcoxon Rank Sum Test). If data has normal distribution, Cohen's d placebo-subtracted effect size will be estimated on mean difference scores from baseline to Visit 13 with confidence intervals.

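### No Visit 13 LSAS rating is fixed for subjects who miss session 2 and no method covers the missing score, so the ITT primary test may omit them; SAP 8.2 can also mislabel exit scores

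*SAP*

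**What the plan says.** - **Endpoint and test.** SAP 8.10.1 takes the "change from baseline to the primary outcome timepoint (visit 13, one month post experimental session 2) in the LSAS score" and compares arms with "independent sample t-tests at an alpha level of 0.05". SAP 8.0 adds: "All statistical tests will be two-sided". Section 8.10.1 does not name its analysis set.
- **Analysis sets.** SAP 8.1 defines ITT as everyone randomised. SAP 8.4 says ITT covers everyone enrolled, using whatever data exist. Protocol 5.4 does not replace subjects who leave after session 1 and promises an intent-to-treat analysis that includes them.
- **What subjects without session 2 are asked for.** Protocol 5.4 asks for integrative sessions, "outcome assessments prior to discontinuation and complete the six-month follow-up assessment if possible". Protocol 12.0 says they "will be asked to complete the final outcome assessment prior to continuing to the 6-month follow-up whenever possible". Protocol 5.2.7 extends the follow-up assessments, including the mailed questionnaires and the independent-rater LSAS at six months, to subjects who left treatment but stayed in follow-up.
- **How the visits are dated.** Visit 13 falls one month after session 2. Protocol Table 2 (section 4.1) dates Visit 14 as "6 Months after V10", and V10 is session 2.
- **Missing data.** SAP 8.2 has two sentences. Early-termination data go to the nearest scheduled visit, and then: "If the closest visit has valid data, the early termination data will be assigned to the next available visit". No imputation or model is given for a missing Visit 13 LSAS. Protocol 12.0 replaces missing responses with the sample mean, but in the paragraph on averaged self-report scores, which does not list the LSAS.
- **A different ITT rule.** Protocol 12.0 would combine early stoppers with completers only if their data are found equivalent, and then only for an exploratory ITT estimate.

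**The concern.** The primary t-test can use a subject only if there is an LSAS value at Visit 13. For a subject who had session 1 but not session 2, Visits 13 and 14 are defined by a session that did not happen. The requested final assessment has no stated time, and nothing says what to do if the Visit 13 score is absent. An analysis labelled ITT could then be run on completers plus whichever stoppers happened to be rated at the right time.

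The protocol foresees such subjects. Sections 2.4, 7.2.1 and 7.2.6 describe circumstances in which a subject has no further experimental session, and 2.4 and 7.2.1 explicitly keep such subjects in follow-up. Those circumstances could be more frequent on MDMA, while stopping for lack of effect could be more frequent on placebo. The study's stated product is an effect size for planning later trials, and with four placebo subjects one omission matters.

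The forward shift in SAP 8.2 is a second, separate problem. It gives a score a visit label that does not match when it was taken or what treatment preceded it.

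**Working it through.** The plan states no power or dropout figure, so there is none to reproduce.

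**Step 1. Visit days.** From Protocol Table 2, assuming a 30-day month and session 1 (V6) at day 0: V7 = 1, V8 = 15, V9 = 29, V10 (session 2) = 30, V11 = 31, V12 = 45, V13 = 59, V14 about 212. LSAS is rated at V7, V8, V9, V11, V12, V13 and V14, not at V10.

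**Step 2. Apply SAP 8.2.** Next available visit is read as the next LSAS visit without a score.

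| LSAS ratings already held | Day of separate exit LSAS | Visit label under 8.2 |
|---|---|---|
| V7 | 1–22 | V8 |
| V7 | 23–30 | V9 |
| V7, V8 | 15–30 | V9 |
| V7, V8, V9 | 29–38 | V11 |
| V7, V8, V9 | 39–52 | V12 |
| V7, V8, V9 | 53–135 | V13 |
| V7–V9, V11, V12 (session 2 given) | 46–51 | V13 |

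Three results follow.
- An exit on day 29 or 30, after V9 and before or at the planned session 2 date, is labelled V11, one day after a session never given.
- For every exit up to day 30, V13 stays empty, including the rows where the label is V8 or V9. The gap comes from having no fixed V13 rating and no missing-data method, not from the shift. A stopper fills V13 only if the final assessment falls at about days 53–135.
- In the last row V12 is nearest but occupied, so the score becomes the primary-endpoint value. On day 46 that is 46 − 30 = 16 days after session 2, against 59 − 30 = 29 days for V13: 13 days early.

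**Step 3. Size of one loss.** Allocation is 8:4 (Protocol 5.3).
- Share of the arm: 1/8 = 12.5% (MDMA) or 1/4 = 25% (placebo).
- Standard error of the difference, common SD, proportional to √(1/n₁ + 1/n₂):
  - 8 v 3 against 8 v 4: √(0.4583/0.375) = 1.106, about 11% wider.
  - 7 v 4 against 8 v 4: √(0.3929/0.375) = 1.024, about 2% wider.
- Effect size detectable at 80% power (two-sided 0.05, noncentral t): 1.90 for 8 v 4, 1.97 for 7 v 4, 2.13 for 8 v 3. These only give scale, since the study claims no power.

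**Step 4. Possible shift of an arm mean.** If the omitted subject's change is Δ points worse than the mean of the others, the mean over all n differs from the mean over the rest by Δ/n. The documents give no Δ, so a range is shown.

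| Δ (assumed) | MDMA, Δ/8 | Placebo, Δ/4 |
|---|---|---|
| 10 | 1.25 | 2.5 |
| 20 | 2.5 | 5.0 |
| 30 | 3.75 | 7.5 |

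The moderate, marked and severe LSAS bands in Protocol 5.1.2 are 10 to 15 points wide.

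**The case against.** The strongest reply is that the protocol follows these subjects well. They may already have V7, V8 and V9 ratings. They are asked for integrative sessions, outcome assessments and the six-month visit. The final outcome assessment in Protocol 12.0 can be read as the V13 battery, because the protocol elsewhere uses similar words for the assessment one month after session 2. If done near the planned date, it would be labelled V13. Protocol 4.0 already requires outcome assessments before session 2, so V9 may itself be the assessment before discontinuation, and then 8.2 has nothing to shift. Someone who stops treatment but stays in follow-up may have no early-termination visit at all. Finally, this is an exploratory, unpowered pilot.

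Much of this stands, and it rules out four stronger readings that a reader might infer.
- *Stoppers are assessed only on exit.* Protocol 5.2.7, 5.4 and 12.0 say otherwise.
- *The 8.2 shift is what empties V13.* Step 2 shows V13 is empty with or without it.
- *V13 and V14 cannot be dated.* V10 is scheduled about one month after V6, so planned dates can be derived. The documents do not say to use them.
- *The estimate is biased.* No dropout pattern or outcome difference is given.

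What the reply does not supply is a time for the final assessment or a rule for a missing V13 score. Protocol 5.4, which places assessments before discontinuation, points to an earlier time than the favourable reading of 12.0. The equivalence route in 12.0 does not fill the gap: equivalence cannot be shown on one or two subjects, and the SAP does not carry the rule. Pilot status lowers the stakes for testing, but not for the effect-size estimate.

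**Conclusion.** The concern holds in this form. For subjects dosed at session 1 who miss session 2, no LSAS rating is fixed at the Visit 13 time and no method covers its absence, so the ITT primary test may become an available-case comparison. One loss removes 12.5% of the MDMA arm or 25% of the placebo arm; a placebo loss widens the standard error by about 11%. Bias is possible, not shown. The 2.5- and 5-point shifts rest on an assumed 20-point difference.

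The mislabelling under SAP 8.2 is separate. For an exit after V9 it affects visit-level summaries and plots, because the planned tests do not use V11. For an exit shortly after V12 it reaches the primary analysis. Both cases assume a separate exit LSAS and the visit days in Step 1. It is worth correcting before analysis but is not a fatal defect.

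**What to change.** 1. **Protocol 5.4, 12.0 and Table 2.** State that a subject dosed at V6 who does not receive session 2 has the blinded independent-rater LSAS and the V13 battery at the planned V13 time, about two months after V6. Visit 14 follows about seven months after V6. Record these as V13 and V14, with a flag that session 2 was not given. Protocol 5.4 already keeps the blind for these subjects to six months, so a blinded rating is feasible.
2. **SAP 8.2.** Replace the forward shift with assignment by actual study day within stated visit windows. Where two values fall in one window, use the one nearest the target day. Never label a score as post-session-2 if it was taken before the planned session 2 date and session 2 was not given.
3. **SAP 8.10.1 with 8.1 and 8.4.** Name the analysis set for the primary test and state one primary method for a V13 LSAS that is still missing. One option is a repeated-measures model on all LSAS ratings with a simple covariance structure, given 12 subjects. Add a sensitivity analysis that varies the missing value over a stated range, as in Step 4. Reconcile this with the equivalence-then-pool rule in Protocol 12.0, and make 8.1 (randomised) and 8.4 (enrolled) agree.

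The cost is wording plus one outcome visit per stopper with the existing rater and forms. Some stoppers will decline, which is why item 3 is needed as well as item 1. A V13 rating from a stopper describes outcome as randomised, including any psychiatric medication resumed by then, and the report should say so.
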